10.2.8. Day 169 (Week 24 ± 3 days) Visit

The Week 24 visit will be the end of study visit for patients who do not choose to continue participating in the optional blinded extension period. After all Week 24 visit procedures have been completed, patients who choose to continue will be re-consented and re-randomized in a blinded fashion to receive the RPC1063 dose titration regimen (if on placebo) or continue on their RPC1063 treatment assignment. First dose monitoring procedures will be followed in all patients as described in [Section 10.2.1](#). Patients participating in the optional blinded extension period will be instructed that they must take the first study drug dose at the clinic before 12:00 pm (noon). The first dose and cardiac monitoring procedures for the blinded extension treatment will be performed on a separate day up to 7 days following the Week 24 visit.

The following assessments will be performed at the Day 169 (Week 24) visit:

- Blood/urine sampling for the following laboratory tests:

- Hematology: RBC count, total and differential WBC count (basophils, eosinophils, lymphocytes, monocytes, and neutrophils), platelet count, hemoglobin, hematocrit, MCV, MCH, and MCHC
Note: All total WBC and differential WBC counts will be blinded during the study.
- Blood chemistry: sodium, potassium, chloride, calcium, magnesium, phosphate, blood urea nitrogen, random glucose, albumin, alkaline phosphatase, creatinine, SGPT/ALT, SGOT/AST, GGT, amylase, total bilirubin, conjugated bilirubin,. Abnormal laboratory parameters inconsistent with clinical presentation of MS or suspicious of underlying medical condition should be repeated for accuracy. If an increase of amylase above the clinically notable value (≥ 300 U/L) is observed at any post randomization visit, lipase should be tested to determine the origin of elevated amylase (pancreatic versus extra pancreatic)
- Urinalysis: leukocytes, specific gravity, bilirubin, blood, glucose, ketones, pH, protein, and urobilinogen
- Urine beta-hCG (females of childbearing potential only). If the urine pregnancy test is positive, do not dose and confirm with a serum pregnancy test.
- Coagulation panel: PT and PTT
- sTSH
- [REDACTED]
- [REDACTED]
- Standard PK sampling: PK samples are to be taken 2 to 6 hours following administration
- Complete physical examination: including evaluation of heart, lung, head and neck, abdominal, neurological, skin, and extremities
- Weight
- Vital signs: body temperature, blood pressure and heart rate. For patients who choose to continue on the blinded extension period, the first dose monitoring procedures must be performed, including recording of baseline (predose) heart rate and blood pressure (see [Section 10.2.1](#))
- 12-lead ECG. For patients who choose to continue on the blinded extension period, the Day 1 first dose monitoring procedures must be performed (see [Section 10.2.1](#)).
- Review study drug accountability and compliance
- Randomize in case patient chooses to continue on the blinded extension period
- If the patient chooses to continue in the study to the blinded extension period, dispense study drug (including titration kit) and patient diary, and administer dose of study drug at the site

- Brain MRI
- [REDACTED] and neurological examination.
- [REDACTED]
- MSQOL-54
- Pulmonary function tests including FEV₁ and FVC measurements, and DLCO
- OCT evaluation
- Dermatological examination
- Suicidality assessment using the C-SSRS
- Record concomitant therapy
- Record AEs/SAEs

Patients who terminate study at this visit will be scheduled for a follow-up visit 4 weeks (\pm 5 days) after last dose.

Patients who choose to continue on the blinded extension period will be scheduled for a safety visit 14 days after first dose of the blinded extension period.

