34. Neutrophils < 1500/ μ L
35. Absolute white blood cell (WBC) count < 3500/ μ L; absolute lymphocyte count < 800/ μ L
36. Clinically significant findings on brain MRI scan consistent with conditions other than MS
37. ECG showing any clinically significant abnormality (e.g., acute ischemia, significant heart conduction abnormality (e.g., left bundle branch block)
38. FEV₁ or FVC < 70% of predicted values at screening
39. Presence of > 20 gadolinium-enhancing lesions on baseline brain MRI scan

NUMBER OF PATIENTS:

In Part A, approximately 210 patients (70 per treatment group) will be randomized.
In Part B, approximately 1200 patients (400 per treatment group) will be randomized.
Patients dosed in Part A will be ineligible for participation in Part B.

STUDY TREATMENT(S):

For all patients in both Part A and Part B of the study, initial study treatment will consist of a 7-day dose titration regimen. For patients randomized to receive active treatment with RPC1063 in Part A or Part B,

this regimen will consist of 0.25 mg RPC1063 starting on Day 1 for 4 days, then 0.5 mg RPC1063 starting on Day 5 for 3 days, followed by the assigned treatment level beginning on Day 8.

Part A

Patients will be randomly assigned 1:1:1 on Day 1 to 1 of 3 treatment regimens through Week 24:

- Placebo oral capsule daily
- 0.5 mg RPC1063 oral capsule daily
- 1 mg RPC1063 oral capsule daily

The randomization will be stratified by country.

In the Part A blinded extension period, RPC1063 (0.5 mg or 1 mg) patients who have completed the 24 weeks placebo-controlled treatment period and who choose to participate in the blinded extension period will continue in their respective treatment groups. Placebo patients will be randomized 1:1 to either a 0.5 mg or 1 mg RPC1063 treatment regimen. All patients will undergo a blinded dose titration regimen.

Part B

Patients will be randomized 1:1:1 to receive 1 of the following three regimens for 24 months:

- IFN β -1a 30 μ g IM injection weekly
- 0.5 mg RPC1063 oral capsule daily
- 1 mg RPC1063 oral capsule daily

The randomization will be stratified by baseline EDSS (≤ 3.5 , >3.5) and country.

Part B will use a double-dummy design. Thus, patients randomized to RPC1063 0.5 or 1 mg will also receive weekly matching placebo IM injections and patients randomized to IFN β -1a 30 μ g will also receive daily matching placebo oral capsules.

RPC1063 and placebo will be provided as powder-filled capsules. RPC1063 drug substance is blended with

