Capsule dosing: dosing will be once daily in the morning in fasting conditions (before breakfast).

On days of study visits on which a pre-dose PK sample will be obtained (Day 1 and Week 12 in Part A, Day 1 and Month 12 in Part B), patients should be instructed to withhold the dose and their morning meal until the office visit, and dose will be administered during the visit.

Part A Blinded Extension Period

In the blinded extension period of Part A, patients will receive 1 of the 2 following treatment regimens:

- 0.5 mg RPC1063 oral capsule daily beginning on Week 25
- 1 mg RPC1063 oral capsule daily beginning on Week 25

RPC1063 0.5 mg or 1 mg patients who have completed the 24-week placebo-controlled treatment period and who choose to participate in the blinded extension period will continue in their respective treatment groups.

Placebo patients who have completed the 24-week placebo-controlled treatment period and who choose to participate in the blinded extension period will be randomized 1:1 to either the 0.5 mg or 1 mg RPC1063 treatment regimen.

All patients who participate in the optional blinded extension period will have an initial 7-day dose titration period as shown in [Table 6](#): 0.25 mg RPC1063 starting on Day 1 for 4 days and 0.5 mg RPC1063 starting on Day 5 for 3 days. Day 1 cardiac monitoring procedures will also be performed on the first day of dose titration, as shown in [Table 5](#). (Holter monitoring will not be included in these cardiac monitoring procedures.) Patients will be dosed with their assigned treatment level beginning on Day 8.

Patients who opt to enter the optional, blinded extension period will continue to receive study drug until all patients who choose to participate have received at least 48 weeks of treatment (total of at least 72 weeks, 24 weeks in the placebo-controlled period and at least 48 weeks in the blinded extension).

Treatment in case of relapse is described in [Section 9.1.2.3](#).

Part B

In Part B, patients will be randomized 1:1:1 to receive one of the following 3 regimens:

- IFN β -1a 30 μ g IM injection weekly for 24 months
- 0.5 mg RPC1063 oral capsule daily for 24 months
- 1 mg RPC1063 oral capsule daily for 24 months

Dosing will begin following randomization on Day 1.

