9.5.3. Study Treatment Labeling and Packaging

RPC1063 capsules will be packaged in [REDACTED] (35 capsules per bottle, apart from the titration kits), closed with a [REDACTED] child resistant screw-cap that is induction sealed.

The labeling will be in accordance with GCP and any other local regulatory requirements.

Details unique to Parts A and B are described below.

Part A

CONFIDENTIAL

The information contained herein may not be used, disclosed, or published without the written consent of Receptos.

Similar to RPC1063 capsules, placebo capsules will be packaged in [REDACTED] (35 capsules per bottle for treatment medication capsules, and 12 capsules per bottle in the titration kits), closed with a [REDACTED] child resistant screw-cap that is induction sealed. The cap on the treatment bottles will be white, and the cap on the titration bottles will be blue.

The labeling will be in accordance with GCP and any other local regulatory requirements.

Part B

IFN β -1a and matching placebo injections will be supplied in prefilled syringes, which will be dispensed to patients at each visit and will contain a sufficient supply of IFN β -1a (or matching placebo) for each dosing interval. Treatment kits must be stored in a secure location. Accountability for study treatment is the responsibility of the Investigator. More details concerning this responsibility are included in [Section 9.5.5](#).

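### Section 10.2.8 ties titration at extension entry to former placebo patients, while the synopsis, Table 1 footnote 12, Section 9.5.1 and its own kit instruction apply it to everyone who continues

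*Protocol*

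**What the plan says.** The opening paragraph of Protocol Section 10.2.8 (Week 24 visit, Part A) states that "patients who choose to continue will be re-consented and re-randomized in a blinded fashion", and the sentence goes on "to receive the RPC1063 dose titration regimen (if on placebo) or continue on their RPC1063 treatment assignment". The next sentence begins "First dose monitoring procedures will be followed in all patients as described in" and refers to the first-dose section. The procedure list for the same visit then instructs the site, for a patient who chooses to continue, to "dispense study drug (including titration kit) and patient diary, and administer dose of study drug at the site", with no condition on prior treatment.

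Elsewhere the protocol describes titration at extension entry as follows:

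- Synopsis, Study Treatment(s), Part A: "All patients will undergo a blinded dose titration regimen".
- Section 9.5.1, Part A Blinded Extension Period: "All patients who participate in the optional blinded extension period will have an initial 7-day dose titration period", with Table 6 cited for the steps.
- Table 1 footnote 12: the 7-day titration follows randomization, and the sentence before it covers all extension patients.

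Section 9.1 requires investigators and patients to stay blinded throughout the extension. Section 9.5.2 says that capsules of all strengths and placebo look identical. Section 9.5.3 distinguishes the packaging: treatment bottles have a white cap, and "the cap on the titration bottles will be blue".

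The Part A SAP does not settle the matter. Its Section 8.2 describes only the initial titration, and its Section 2 defers extension analyses to a separate plan.

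**The concern.** Section 10 is the visit-by-visit text that sites follow, so a dosing rule there that differs from Section 9.5.1 can be carried out as written. Two things are at stake.

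The first is dosing. A former RPC1063 patient either restarts at the titration dose or goes on at the assigned dose, depending on which section the site reads.

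The second is the blind in the extension. Titration differs visibly from maintenance in capsule number and in packaging. A scheme that titrated only former placebo patients, with no matching sham titration for the rest, could show who had been on placebo.

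**Working it through.** No statistical figure in the plan depends on this point. The check is a comparison of passages and a hand count from Table 6.

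**Who is titrated at extension entry**

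| Place | Who | Condition on prior treatment |
|---|---|---|
| Synopsis, Part A treatment | All patients | None |
| Section 9.5.1, blinded extension | All extension participants, by Table 6 | None |
| Table 1 footnote 12 | Patients entering the extension | None |
| Section 10.2.8, procedure list | Kit for any patient who continues | None |
| Section 10.2.8, opening paragraph | Former placebo patients | Yes |

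The opening paragraph of 10.2.8 disagrees with three other places and with its own list. Table 6 has no extension rows. The conflict with it arises because Section 9.5.1 applies it to the extension.

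**First-week dose for a former RPC1063 patient** (Table 6: 0.25 mg on Days 1 to 4, 0.5 mg on Days 5 to 7)

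- Titrated: 4 × 0.25 + 3 × 0.5 = 1.0 + 1.5 = 2.5 mg.
- Continuing at 0.5 mg: 7 × 0.5 = 3.5 mg.
- Continuing at 1 mg: 7 × 1 = 7 mg.

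**First-week capsules** (Table 6: one capsule on Days 1 to 4, two on Days 5 to 7, one from Day 8)

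- Titrated: 4 × 1 + 3 × 2 = 10.
- Continuing at the assigned dose: 7 × 1 = 7.

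Identical capsules do not hide the difference between 10 and 7, or the cap colour. By Section 9.5.3, Part A titration bottles also hold 12 capsules and treatment bottles 35.

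**How many patients** (Section 13.2: 70 per arm)

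- Former RPC1063 patients: at most 2 × 70 = 140. Former placebo patients: at most 70.
- If the 15% dropout assumed in Section 13.2 applies before Week 24: 140 × 0.85 = 119 and 70 × 0.85 = 59.5, about 60. Patients who decline the extension lower both figures further.

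**Who is re-randomized.** The sentence in 10.2.8 reads as though every continuing patient is re-randomized. Table 1 footnote 12 and Section 9.5.1 randomize only former placebo patients, 1:1, and keep RPC1063 patients in their groups.

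**The case against.** The best defence is that this is one stray parenthetical. The synopsis, Section 9.5.1 and footnote 12 agree with one another. Continuing on an RPC1063 assignment could loosely mean staying in the same group after a titration. The paragraph also says that re-randomization is blinded, first-dose monitoring covers all patients, and a kit is dispensed to everyone who continues. This makes an intended difference in treatment doubtful. It does not remove the contradiction, because the parenthetical still attaches titration to placebo patients alone.

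Three stronger readings are tempting, and the documents do not support them.

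- **That 10.2.8 would unblind patients.** If every continuing patient receives a titration kit, the kit and blue cap distinguish no one. Table 6 and Section 9.5.3 also show that placebo titration supplies exist in Part A, so a masked titration is possible, although none is described for former RPC1063 patients. The supportable statement is conditional. Even in the worst case, what is exposed is past placebo against past RPC1063, not whether the current dose is 0.5 mg or 1 mg.
- **That the Week 24 primary endpoint is at risk because some patients enter the extension before others finish.** By footnote 12 and Section 10.2.8, each patient completes the Week 24 procedures before the first extension dose, which is given on a separate day. MRI is read centrally by readers blinded to treatment (Sections 9.1.2.2 and 11.1.1). Nothing in the documents shows how one patient's past allocation would reveal another's.
- **That all 210 patients are affected.** The extension is optional and open only to those who complete 24 weeks.

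**Conclusion.** The inconsistency is real and should be corrected. Section 10.2.8 cannot be followed together with Section 9.5.1, and the choice changes first-week exposure for every former RPC1063 patient who enters the extension: 2.5 mg against 3.5 mg or 7 mg, in at most about 140 patients. The documents do not allow a conclusion on which dosing rule is right, and none is offered here.

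The blinding consequence is a possibility. It rests on two assumptions: that titration is limited to former placebo patients, and that nothing masks the capsule count and packaging. Under both, prior placebo assignment could become known to investigators and patients during the extension. The primary analysis of Part A is not directly affected.

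**What to change.** Reconcile the synopsis, Table 1 footnote 12, Section 9.5.1 and both parts of Section 10.2.8 (opening paragraph and procedure list), so that they state one rule on who is titrated at extension entry. The sponsor has to decide that rule.

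State explicitly that kits, bottles and daily capsule counts will look the same to patients and site staff whatever the prior treatment.

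In the same edit, align the Section 10.2.8 wording on who is re-randomized with footnote 12 and Section 9.5.1.

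The cost is protocol wording. Sample size, endpoints and the Part A analyses are unchanged.

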- 9 A chest X-ray is not required if performed within 60 days prior to randomization and if documentation is on file.
- 10 Refer to [Table 5](#) for details of cardiac monitoring.
- 11 At the Week 24 visit (Day 169), cardiac monitoring procedures will also be performed on the first day of dosing for patients who continue in the optional extension period following the first dose of that period. Refer to [Table 5](#) for details of cardiac monitoring.
- 12 At Week 24, patients will be given the option to enter an extension period. The blinded extension study will continue until all patients who choose to participate have received at least 48 weeks of treatment in the extension. Patients assigned to either RPC1063 treatment group during the double-blind placebo-controlled period will continue in their respective treatment groups during the blinded extension; patients assigned to the placebo treatment group will be re-randomized in a 1:1 fashion to receive one of the two RPC1063 treatment groups for the blinded extension. For all patients in the blinded extension, the first dose of study medication will be administered on a separate day after the Week 24 visit procedures are completed, and may be performed up to 7 days after the Week 24 visit date. Upon randomization, the 7-day dose titration regimen will be administered, study medication will be dispensed, and first dose cardiac monitoring procedures will be performed. (See [Table 5](#))
- 13 Three MSFC practice assessments must be performed before baseline. These may be performed at the screening visit, or at any time between the screening and baseline visit.
- 14 Pulmonary function tests will include FEV₁ and FVC measurements at all the above indicated visits. In addition, DLCO (if available locally) will be assessed at screening and Week 24. If any abnormalities occur, they will be followed until such time as resolution is confirmed or no further improvement is expected by the investigator (based on a follow-up period of not less than 3 months).
- 15 If abnormal OCT findings, or visual signs or symptoms of macular edema are observed, a general ophthalmologic examination including eye history, visual acuity, and dilated ophthalmoscopy will also be performed.

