- 16 PK samples on Day 1 and Week 12 will be taken predose. PK samples at Week 4 and Week 24 will be taken 2 to 6 hours following study drug administration; patients should record the time of study drug administration for these visits. An additional PK sample will be obtained for patients with any AE resulting in unblinding, discontinuation, or SAE.

CONFIDENTIAL

The information contained herein may not be used, disclosed, or published without the written consent of Receptos.

Table 2 Schedule of Assessments – Part A: Optional Blinded Extension, Early Termination, and Follow-up Visits

Procedure	Blinded Extension ¹			Un-scheduled Relapse Visit ⁴	Early Term ⁵	Follow Up Visit 4 weeks after last dose (±5d)
	Day 183 (W26) ² (±1d)	Every 12 weeks ³ (±5d)	End of Study ³			
Clinical laboratory tests ⁶		X	X	X	X	X
Urine/serum pregnancy (women of childbearing potential only) ⁷		X	X		X	X
Coagulation panel			X		X	
Total Ig (IgA, IgG, IgM)						
Complete physical examination			X		X	
Weight			X		X	
Vital Signs	X	X	X	X	X	X
12-lead ECG	X	X	X		X	X
Study drug administration	X	X	X			
Administer study drug at clinic						
Dispense study drug and patient diary		X				
Study drug accountability and compliance check	X	X	X		X	
Brain MRI		X ⁸	X ⁸		X	
EDSS and neurological examination		X	X	X	X	
MSFC and LCLA		X	X	X	X	
MSQOL-54			X		X	
Pulmonary function tests ⁹		X	X		X	
OCT ¹⁰			X		X	
Dermatological (skin) examination			X			
C-SSRS	X	X	X	X	X	X
Standard PK sampling ¹¹					X	
Plasma biomarkers						
Prior/Concomitant therapy	X	X	X	X	X	X
AEs/SAEs	X	X	X	X	X	X

ECG = electrocardiogram, MRI = magnetic resonance imaging, EDSS = Expanded Disability Status Scale, MSFC = Multiple Sclerosis Functional Composite, LCLA = low-contrast letter acuity test; MSQOL = Multiple sclerosis quality of life, OCT = optical coherence tomography, C-SSRS = Columbia- Suicide Severity Rating Scale, PK = pharmacokinetics, AE/SAE = adverse events/serious AE

CONFIDENTIAL

The information contained herein may not be used, disclosed, or published without the written consent of Receptos.

Footnotes to Table 2

- 1 The blinded extension is optional.
- 2 A visit for safety assessments will be performed 14 days after the first dose of study medication.

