Additional extended monitoring should be instituted until the finding has resolved in the following situations:

- The heart rate 6 hours post-dose is < 45 bpm
- The heart rate 6 hours post-dose is at the lowest value post-dose (suggesting that the maximum PD effect on the heart may not have occurred)
- The ECG 6 hours post-dose shows new onset second degree or higher AV block
- The ECG 6 hours post-dose shows a prolonged QTcF interval (>450 msec males, >470 msec females).

Should post-dose symptomatic bradycardia occur, the treating neurologist should be notified and he or she should initiate appropriate management, begin continuous ECG monitoring, and continue observation until the symptoms have resolved.

Should a patient require pharmacologic intervention for symptomatic bradycardia, continuous overnight ECG monitoring in a medical facility should be instituted, and the first dose monitoring strategy should be repeated the following day (Day 2). The first dose monitoring strategy should also be repeated at Day 5 if any cardiac safety issues were observed on Day 1.

Patients should have written instruction on when to return to clinic and a 24-hour contact phone number to call in the event of any new or warranted symptoms (e.g., chest pain, dizziness, palpitations, syncope, nausea, vomiting). Patients should be instructed not to drive on the same day after the first dose of study drug administration.

First dose monitoring procedures will also be followed at the Week 24 visit in Part A for patients who elect to continue in the blinded extension study, or for any patient who resumes treatment after missing more than 7 consecutive doses.

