10.2.9. Day 183 (Week 26 \pm 1 day) Visit of the Blinded Extension

This visit will be performed for safety purposes. The following assessments will be performed at the Week 26 visit of the optional blinded extension:

- Vital signs: body temperature, blood pressure and heart rate
- 12-lead ECG
- Review study drug accountability and compliance
- Suicidality assessment using the C-SSRS
- Record concomitant therapy
- Record AEs/SAEs

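### Protocol Section 10.2.8 and the linked tables put the first blinded-extension dose and its cardiac monitoring both at the Week 24 visit and on a separate day

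*Protocol*

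**What the plan says.** Two groups of statements in the protocol cover the same event.

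**Separate day.** The opening paragraph of Section 10.2.8 says that the first extension dose and its cardiac monitoring "will be performed on a separate day up to 7 days following the Week 24 visit". Table 1 footnote 12 (Section 9.1.1) says that "the first dose of study medication will be administered on a separate day after the Week 24 visit procedures are completed", again allowing up to 7 days.

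**Week 24 visit.** The line after that opening paragraph introduces the procedure list with "The following assessments will be performed at the Day 169 (Week 24) visit". For patients who continue, the list contains re-randomization, first-dose monitoring with a predose heart rate and blood pressure, the Day 1 ECG procedures, and the instruction to "dispense study drug (including titration kit) and patient diary, and administer dose of study drug at the site". Section 10.2.1.1 says "First dose monitoring procedures will also be followed at the Week 24 visit in Part A". Table 5 uses one monitoring column for both Day 1 and Part A Day 169 (Week 24).

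Table 1 footnote 11 names both the Week 24 visit and the first day of dosing in one sentence, so it settles nothing.

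Two further rules bear on the Week 24 day. Table 1 footnote 16 says "PK samples at Week 4 and Week 24 will be taken 2 to 6 hours following study drug administration", and Section 10 times such visits to the patient's usual dosing time. Sections 9.5.1 and 10 name the Part A visits at which the patient holds back the home dose: Day 1 and Week 12, not Week 24.

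For the next visit, Table 2 footnote 2 says "A visit for safety assessments will be performed 14 days after the first dose of study medication", and the end of Section 10.2.8 agrees. Section 10.2.9 and the Table 2 column heading label that visit Day 183, with a window of 1 day either side.

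**The concern.** Sites tend to work from visit lists and schedule tables. Here those point to dosing and monitoring at Week 24, while a paragraph and a footnote point to another day. The procedure in question is first-dose cardiac monitoring, where the date of the dose and the meaning of predose have to be unambiguous.

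If a site follows the list on a day when the patient has already taken the double-blind dose, two things follow for an RPC1063 patient. The day's total exceeds the assigned dose, and the cardiac baseline is taken on recently dosed active drug. Sites that read the text differently would also produce extension first-dose data under different conditions. The Week 26 safety visit inherits the problem, because one of its two anchors moves with the first dose and the other does not.

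**Working it through.** The plan gives no figure on this point, so there is none to reproduce. The check is a comparison of the text plus simple arithmetic.

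**1. Where each place puts the event**

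| Place in protocol | First extension dose | First-dose monitoring |
|---|---|---|
| 10.2.8, opening paragraph | Separate day, up to 7 days later | Same separate day |
| Table 1 footnote 12 | Separate day, up to 7 days later | With the titration start, no day named |
| 10.2.8, procedure list | At the Week 24 visit | At the Week 24 visit, with predose values |
| 10.2.1.1 | Not stated | At the Week 24 visit |
| Table 5 heading | Not stated | Day 169 (Week 24) |

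The first and third rows are in the same section and cannot both be followed.

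**2. Would the patient already have dosed?** Yes, on the text. Week 24 is not a withheld-dose visit (Sections 9.5.1 and 10), and its PK sample is due 2 to 6 hours after the dose.

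**3. Same-day total.** Section 9.5.1 starts extension titration at 0.25 mg for all patients.
- 0.5 mg arm: 0.5 + 0.25 = 0.75 mg, which is 0.75 / 0.5 = 1.5 times the assigned dose.
- 1 mg arm: 1 + 0.25 = 1.25 mg, which is 1.25 times the assigned dose.
- Placebo arm: 0 + 0.25 = 0.25 mg, the intended titration dose.

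**4. Drug on board at the baseline.** Section 7.2.4 gives a half-life of about 18 to 21 hours in healthy volunteers. Assuming simple mono-exponential decline, the share of one dose remaining is 0.5^(hours / half-life).
- 2 hours: 0.93 to 0.94. 6 hours: 0.79 to 0.82. So about 79 to 94% remains at 2 to 6 hours.
- 24 hours: 0.40 to 0.45. 168 hours (7 days, no dose in between): 0.002 to 0.004.

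At steady state on once-daily dosing, accumulation is 1 / (1 − 0.5^(24 / half-life)) = 1.66 to 1.83. The amount left 24 hours after the last dose is 1.66 × 0.397 = 0.66 to 1.83 × 0.453 = 0.83 of a daily dose. That is 0.66 to 0.83 mg in the 1 mg arm and 0.33 to 0.41 mg in the 0.5 mg arm.

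**5. Week 26 anchors.** The Day 183 window is Days 182 to 184. A visit 14 days after the first dose falls in that window only for a first dose on Days 168 to 170.
- First dose on Day 169: 169 + 14 = Day 183. The anchors agree.
- First dose on Day 176 (169 + 7): 176 + 14 = Day 190, which is 190 − 184 = 6 days past the window. A visit held on Day 183 would be only 7 days after the first dose.
- With Week 24 at ± 3 days (Days 166 to 172) and a gap of 1 to 7 days, the 14-day visit falls between Day 166 + 1 + 14 = 181 and Day 172 + 7 + 14 = 193.

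**6. Patients concerned.** The total exceeds the assigned dose only in the two RPC1063 arms: 140 randomized, and 140 × 0.85 = 119 completers at the plan's 15% dropout, if all enter the extension.

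**The case against.** The strongest reply is that the timing is stated outright. The opening paragraph and footnote 12 both say a separate day, and in Table 1 footnote 12 is attached to the Week 24 marks for randomization, drug administration and dispensing. Section 9.5.1 ties monitoring to the first day of titration. The disputed list items apply only to patients who continue. A same-day dose is also awkward. It would have to be given at the clinic before noon, in a fasted state, after the Week 24 procedures, re-consent and re-randomization; for the earliest 2-hour PK sample to precede it, the home dose would have to be taken before 10 a.m. For Week 26, Section 10 lets windows be stretched case by case, except for MRI and EDSS and for visits during titration; this visit has neither assessment and, at 14 days, falls after the 7-day titration.

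This stands as far as it goes. A careful site may well use a separate day, and the Week 26 mismatch is softened. But the list still directs dosing at the Week 24 visit, and Section 10.2.1.1 and Table 5 support that reading for monitoring.

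A reader might infer more than the documents support:
- **That the Week 24 PK level would reflect 0.25 mg in every arm.** Section 10.2.8 puts re-randomization after all Week 24 procedures, Section 10 keys the sample to the usual dosing time, and nothing tells patients to withhold the dose. Even if it were withheld, carry-over in the RPC1063 arms (working, step 4) would exceed 0.25 mg.
- **That a same-day double dose is an overdose under Section 12.8.** That definition refers to the dose described in the protocol; it does not clearly cover two doses that the protocol's own text leads a site to give.
- **That the conflict itself biases a comparison between arms.** No washout is stated, so RPC1063 patients may have a drug-exposed baseline on the separate-day reading too. SAP Section 2 leaves extension analyses to another plan, Section 10 has no safety hypothesis tests, and Section 10.3 uses the Day 1 predose value as the vital-sign baseline.
- **That all 210 patients are affected.** The extension is optional and open to completers only.

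**Conclusion.** The contradiction is real and affects conduct: the protocol gives two incompatible days for the first extension dose and its cardiac monitoring. On the same-day reading, an RPC1063 patient could receive 0.75 or 1.25 mg in one day and have a predose cardiac baseline recorded hours after active drug. This is a risk of inconsistent conduct among at most about 119 RPC1063 patients, not an error certain to occur. The two Week 26 anchors agree only for a first dose within a day of Day 169, and the window rule in Section 10 reduces the practical effect.

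The result assumes that a site follows the procedure list literally, that the patient has taken the usual morning dose, and that titration starts at 0.25 mg for every extension patient as Section 9.5.1 says. The opening paragraph of Section 10.2.8 links titration to placebo patients only, so that wording needs reconciling too. The drug-on-board figures also rest on the healthy-volunteer half-life and a simple decay model. I take no position on which day, dose or monitoring rule is right.

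**What to change.** The sponsor should:
- reconcile both parts of Section 10.2.8, Section 10.2.1.1, Table 1 footnotes 11 and 12, and the Table 5 column heading, so that one rule names the day of the first extension dose and its monitoring;
- place the dosing, predose vital sign, ECG and monitoring lines under the day that the rule names;
- state which dose the Week 24 PK sample refers to;
- give the Week 26 visit one anchor in Section 10.2.9, Table 2 and the end of Section 10.2.8.

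The same edit can say whether study drug is taken during any gap between Week 24 and the first extension dose, which the text leaves open. The cost is wording and a notice to sites; no procedure is added.
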